7.3 Secondary Objectives

- To assess the efficacy of Healsea® Chronic in improving health-related quality of life of CRS adult patients.
- To assess the global satisfaction of patients in using Healsea® Chronic nasal spray for CRS.
- Safety: to assess systemic and local tolerance of Healsea® Chronic over the study period.

7.4 Scientific justification and clinical relevance for effect sizes, non inferiority margins or equivalence

Not applicable. This is an exploratory clinical investigation.

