8.5.2 Monitoring

Study monitoring under responsibility of Lallemand Pharma by qualified staff will be performed at various stages of the study. Monitoring will include on-site visits and centralized data review to assure that the investigation is conducted according to the CIP and comply with applicable regulations and deadlines. On-site review of Case Report Form (paper CRFs) will include the review of forms for completeness, clarity and consistency with source documents available for each subject. In case of queries, the investigator should respond within agreed timelines.

The investigator must permit study-related monitoring visits, audits review by the Ethic Committee and ANSM, and allow direct access to source data and source documents provided that subject confidentiality is protected. In case of an audit appointed by Lallemand Pharma, the investigator will receive written notification in advance.

9. Statistical design and analysis

Patients and disease characteristics will be described at baseline.

16S rRNA Gene Sequence Analysis

The normal distribution of the values is verified thanks to normality tests (e.g. Shapiro-Wilk test). However, it is most likely that the group size will be insufficient to apply parametric statistical tests. Significant variations in total number of bacterial 16S rRNA gene copies or in alpha diversity are assessed using the Kruskal-Wallis test or the Wilcoxon rank-sum test. Multidimensional scaling analyses (MDS) are performed on beta diversity distances matrices and differences between groups were assessed using PERMANOVA and PERMDISP analyses (2000 permutations). LEfSe (Linear discriminant analysis Effect Size) analyses, based on non-parametric tests are used to determine significant variations in taxa relative abundance [17].

Secondary endpoints

Values and changes from baseline to D30/end of study of the SNOT-22 total score will be described.

Patients satisfaction will be described at D30/end of study.

Safety

All adverse events/incidents/expected side effects will be listed, but only treatment-emergent adverse events/incidents (non-serious + serious) and expected side effects will be summarized by the number and percentage of patients, classified by System Organ Class and Preferred Term as defined by MedDRA dictionary.

Frequency and percentage of patients with at least one reported adverse event/incident/expected side effect will be tabulated by System Organ Class.

10. Data collection

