16.1 Definitions

Incident means any malfunction or deterioration in the characteristics or performance of a device made available on the market, including use-error due to ergonomic features, as well as any inadequacy in the information supplied by the manufacturer and any undesirable side-effect (MDR 2017/745, article 2 (64)).

Serious incident means any incident that directly or indirectly led, might have led or might lead to any of the following: (a) the death of a patient, user or other person, (b) the temporary or permanent serious deterioration of a patient's, user's or other person's state of health, (c) a serious public health threat (MDR 2017/745, article 2(65)).

Serious public health threat means an event which could result in imminent risk of death, serious deterioration in a person's state of health, or serious illness, that may require prompt remedial action, and that may cause significant morbidity or mortality in humans, or that is unusual or unexpected for the given place and time (MDR 2017/745, article 2(66)).

Expected and foreseeable side effects (MEDDEV 2 12-1 rev. 8)

They meet all the following criteria:

- Clearly identified in the manufacturer's labelling;
- Clinically well known as being foreseeable and having a certain qualitative and quantitative predictability when the device is used and performs as intended;
- Documented in the device master record, with an appropriate risk assessment, prior to the occurrence of the incident and
- Clinically acceptable in terms of the individual patient benefit.

Adverse event means any untoward medical occurrence, unintended disease or injury or any untoward clinical signs, including an abnormal laboratory finding, in subjects, users or other persons, in the context of a clinical investigation, whether related or not related to the investigational device (MDR 2017/745, article 2(57)).

Adverse or intercurrent events are graded as follows:

- Mild: Awareness of signs or symptoms but easily tolerated.
- Moderate: Uncomfortable enough to cause interference with usual activity.
- Severe: Incapacity with inability to work or do usual activity.

Serious Adverse Event means any adverse event that led to any of the following:

- (a) death,
- (b) serious deterioration in the health of the subject, that resulted in any of the following:
 - (i) life-threatening illness or injury,
 - (ii) permanent impairment of a body structure or a body function,

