11.2. Adverse events

Note: in the following paragraph, for a smoother reading:

- Incidents and adverse events will be referred as adverse events (AE);
- treatment-emergent incidents and adverse events will be referred as treatment-emergent adverse event (TEAE).

AE are coded using the MedDRA dictionary version 25.0. They are classified by System Organ Class and Preferred Term.

An AE will be considered as a TEAE if:

- it was not present prior to the reference start date
- it was present prior to the reference start date and worsened during the study (increase of intensity)
- it reappears after the reference start date (finished before the reference end date)

A given TEAE (according to the MedDRA terminology) will be counted only once per subject. If a subject experienced several AEs in the same SOC/PT, the most severe intensity will be retained for this SOC/PT.

Note: if the intensity/severity is missing, a conservative approach will be adopted and the intensity/severity will be considered as severe.

Missing or incomplete dates will be estimated as described in section §6.4.4 in order to determine the TEAEs, but they will be presented as reported in CRF in the data listings. Generally, an AE for which the onset date is missing or incomplete and does not permit to identify the onset according to the date of the reference start date (i.e. missing onset day and month/year corresponding to the reference start date) will be considered as treatment-emergent.

Tables will present separately:

- **incidents related to the use of the medical device** (described as possibly related, probably related or related with the device in the eCRF),
- **adverse events not related to the use of the medical device**

- Summary of adverse-events

Summary tables will be produced for AEs not related to the use of medical device and for incidents related to the use of the medical device. Tables will be adapted depending on the definition of the type of AE

- number and percentage of subjects with at least one adverse event (AE)
- number and percentage of subjects with at least one AE leading to definitive study device discontinuation
- number and percentage of subjects with at least one AE leading to definitive study discontinuation
- number and percentage of subjects with at least one serious adverse event (SAE)
- number and percentage of subjects with at least one TEAE
 - number and percentage of subjects with one TEAE
 - number and percentage of subjects with two TEAE

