XXXX sino-nasal symptom – End of study	
N	XX
Missing	XX
Yes	XX (XX.X%)
No	XX (XX.X%)
XXXX sino-nasal symptom – Change from baseline	
N	XX
Missing	XX
Improvement	XX (XX.X%)
No change – symptom present	XX (XX.X%)
No change – symptom absent	XX (XX.X%)
Degradation	XX (XX.X%)

Table 14.2.4. Safety - Secondary efficacy criteria – Weight of device [FAS]

Healsea Chronic N=XX	
Returned device	
N	XX
Missing	XX
Yes	XX (XX.X%)
No	XX (XX.X%)
Weight of returned device	
N	XX
Missing	XX
Mean (SD)	XX.X (XX.X)
Median	XX
Q1/Q3	XX / XX
Min/Max	XX / XX

Table 14.3.1.1. Safety - Study duration by subject [Safety Set]

Healsea Chronic N=XX	
Study duration (days)	
N	XX
Missing	XX
Mean (SD)	XX.X (XX.X)
Median	XX
Q1/Q3	XX / XX
Min/Max	XX / XX

Table 14.3.1.2. Safety - Summary of compliance [Safety Set]

Healsea Chronic N=XX	
Compliance (%)	
N	XX
Missing	XX
Mean (SD)	XX.X (XX.X)
Median	XX
Q1/Q3	XX / XX
Min/Max	XX / XX

Table 14.3.1.3. Safety – Concomitant treatments [Safety Set]

ATC1 - ATC2	Healsea Chronic N=XX
Subjects with at least one concomitant treatment	
All	XX (XX.X%)
XXXXXX	
All	XX (XX.X%)
XXXXX	XX (XX.X%)
XXXXX	XX (XX.X%)

Table 14.3.2.1 Safety – Brief summary of incidents related to the use of the medical device [Safety Set]

Number and percentage of subjects with related / Number of related	Healsea Chronic N=XX	
	n (%)	[E]
Incident	XX (XX.X%)	XXX
Incident leading to definitive study device discontinuation	XX (XX.X%)	XXX
Incident leading to definitive study discontinuation	XX (XX.X%)	XXX
Serious incident	XX (XX.X%)	XXX
At least one treatment-emergent incident	XX (XX.X%)	XXX
Exactly one treatment-emergent incident	XX (XX.X%)	XXX
Exactly two treatment-emergent incident	XX (XX.X%)	XXX
At least three treatment-emergent incidents	XX (XX.X%)	XXX

Table 14.3.2.2 Safety – Brief summary of adverse events not related to the use of the medical device [Safety Set]

		Healsea Chronic N=XX	
		n (%)	[E]
Number and percentage of subjects with related / Number of related			
Incident		XX (XX.X%)	XXX
Incident leading to definitive study device discontinuation		XX (XX.X%)	XXX
Incident leading to definitive study discontinuation		XX (XX.X%)	XXX
Serious incident		XX (XX.X%)	XXX
At least one treatment-emergent incident		XX (XX.X%)	XXX
Exactly one treatment-emergent incident		XX (XX.X%)	XXX
Exactly two treatment-emergent incident		XX (XX.X%)	XXX
At least three treatment-emergent incidents		XX (XX.X%)	XXX

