Table 14.3.2.3. Safety – TEAE (incidents) related to the use of the medical device by System Organ Class and preferred term [Safety Set]

		Healsea Chronic N=XX	
		n (%)	[E]
Related treatment-emergent adverse events			
All		XX (XX.X%)	XXX
XXXXXX			
All		XX (XX.X%)	XXX
XXXXXX		XX (XX.X%)	XXX
XXXXXX		XX (XX.X%)	XXX

Table 14.3.2.4. Safety – TEAE not related to the use of the medical device by System Organ Class and preferred term [Safety Set]

		Healsea Chronic N=XX	
		n (%)	[E]
Related treatment-emergent adverse events			
All		XX (XX.X%)	XXX
XXXXXX			
All		XX (XX.X%)	XXX
XXXXXX		XX (XX.X%)	XXX
XXXXXX		XX (XX.X%)	XXX

Table 14.3.2.5. Safety – Serious TEAE (incidents) related to the use of the medical device by System Organ Class and preferred term [Safety Set]

		Healsea Chronic N=XX	
SOC - Preferred Term	n (%)	[E]	
Related treatment-emergent adverse events			
All	XX (XX.X%)	XXX	
XXXXX			
All	XX (XX.X%)	XXX	
XXXXX	XX (XX.X%)	XXX	
XXXXX	XX (XX.X%)	XXX	

Table 14.3.2.6. Safety – Serious TEAE not related to the use of the medical device by System Organ Class and preferred term [Safety Set]

		Healsea Chronic N=XX	
SOC - Preferred Term	n (%)	[E]	
Related treatment-emergent adverse events			
All	XX (XX.X%)	XXX	
XXXXX			
All	XX (XX.X%)	XXX	
XXXXX	XX (XX.X%)	XXX	
XXXXX	XX (XX.X%)	XXX	

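### Every on-study adverse event table in the SAP is split by device-relatedness, so none gives the pooled patient count that protocol section 9 most naturally describes, and the three 'not related' shells are headed 'related'

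*Protocol*

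**What the plan says.** Tolerance is a stated secondary objective (protocol 7.3): "Safety: to assess systemic and local tolerance of Healsea® Chronic over the study period". For its analysis, protocol section 9 (repeated in the synopsis) says: "All adverse events/incidents/expected side effects will be listed, but only treatment-emergent adverse events/incidents (non-serious + serious) and expected side effects will be summarized", by SOC and PT. It then adds: "Frequency and percentage of patients with at least one reported adverse event/incident/expected side effect will be tabulated by System Organ Class". Neither sentence mentions a split by relatedness.

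SAP 11.2 introduces its safety output with "Tables will present separately" and names two groups: incidents related to the device, and adverse events not related to it. The list in SAP 13.2 follows that division. It has two brief summaries (14.3.2.1, 14.3.2.2), two SOC/PT tables (14.3.2.3, 14.3.2.4) and two SOC/PT tables of serious events (14.3.2.5, 14.3.2.6). SAP section 12 explains that, after data review, the display went from three categories to these two.

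On intensity, protocol 16.1 defines three grades ("Adverse or intercurrent events are graded as follows": mild, moderate, severe). SAP 11.2 treats missing intensity as severe and adds: "If a subject experienced several AEs in the same SOC/PT, the most severe intensity will be retained for this SOC/PT".

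**The concern.** A patient with one device-related incident and one unrelated event appears in both halves of the display. The number of patients with any event is therefore not the sum of the two columns, and no listed on-study table reports it. That number is the simplest answer to the tolerance objective. In an open, single-arm study it is also the figure that does not depend on an unblinded judgement of causality.

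Two related defects affect the same outputs. The SAP sets a rule for reducing repeated events to the worst grade, but no listed table shows a grade. And the shells for unrelated events contradict their own titles, so a programmer following the shell and one following the title would label the same numbers differently.

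**Working it through.** The plan gives no safety figure to reproduce, so the check compares the texts and then bounds the missing count.

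**1. Tables against the protocol sentence.** Of the six on-study adverse event tables in SAP 13.2, six are split by device-relatedness and none pools the two groups. The only adverse event table without the split, 14.1.2.5.1, is a baseline table on the FAS. It does not cover the study period and is not on the Safety Set. Section 12 describes a move from three display categories to two. A pooled count is neither of these, and section 12 does not mention dropping one.

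**2. What can be recovered from the split tables.** Let *a* be the subjects with a device-related incident, *b* the subjects with an unrelated event, and *N* the Safety Set size. Subjects with any event lie between max(*a*, *b*), where the overlap is complete, and min(*N*, *a* + *b*), where the overlap is as small as possible. The documents give no event counts, so *a* and *b* below are assumed. *N* = 20 is the planned number (protocol 8.3.6, SAP section 4).

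| *a* | *b* | Lower bound | Upper bound | Range |
|---|---|---|---|---|
| 2 | 5 | max(2, 5) = 5 | min(20, 7) = 7 | 25% to 35% |
| 6 | 8 | max(6, 8) = 8 | min(20, 14) = 14 | 40% to 70% |
| 8 | 12 | max(8, 12) = 12 | min(20, 20) = 20 | 60% to 100% |

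The same bounds apply within each SOC. If either count is zero, the overall count is exact; the range widens as both groups fill. The event counts in the [E] columns can be added, because an event falls in one group only, but the protocol sentence is about patients.

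**3. Intensity.** None of the six shells has a row or column for intensity. The worst-grade rule therefore has no display.

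**4. Titles against headings in the shells (SAP 13.3).**

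| Table | Title | Heading in the shell |
|---|---|---|
| 14.3.2.2 | Brief summary, events not related | "Number and percentage of subjects with related / Number of related" |
| 14.3.2.4 | TEAEs not related | "Related treatment-emergent adverse events" |
| 14.3.2.6 | Serious TEAEs not related | "Related treatment-emergent adverse events" |

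All three unrelated-event shells are affected. The rows of 14.3.2.2 also read *Incident*, the word that SAP 11.2 attaches to device-related events when it defines the two groups.

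**5. SAP 11.2 against 13.2.** Among the SOC/PT tables, 11.2 still names one for CRS-related events and one for swab-related events. Neither is in 13.2. In the other direction, 13.2 lists an unrelated-event SOC/PT table that is missing from the SOC/PT list in 11.2.

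**The case against.** The protocol sentence joins the event types with slashes and does not say pooled or overall, so one table per event type is a possible reading. This stands as a caveat. Pooled is still the more natural reading, and the split in the SAP follows relatedness to the device, which the sentence does not mention.

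Section 12 declares the two-category display openly. That is right, and the change itself is not an error. But it does not tell the reader that no all-event count will be given.

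The tables are not the only safety output. SAP 11.2 plans listings of deaths, serious events and discontinuations and refers to data listings generally, and the protocol wants every event listed. With about 20 patients, a full listing would let a reader count by hand. However, the subject data listings shown in 13.2 (16.2.1 to 16.2.6) include none for adverse events, so the limitation holds for the planned tables and is not clearly cured elsewhere.

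The study is exploratory and descriptive, has no comparator against which to judge an all-cause rate, and hides neither group. This limits the importance of the point but does not remove it.

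Four stronger readings are tempting and not supported:

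- A reader might infer that the SAP drops a severity analysis that the protocol promised. Protocol 16.1 defines grades, but section 9 plans no severity table.
- A reader might infer that intensity is not used at all. It is: under SAP 11.2, a pre-existing event that worsens in intensity becomes treatment-emergent. What is missing is any display of it.
- A reader might infer from the wrong headings that unrelated events would be filtered out and lost. The titles are correct in both 13.2 and 13.3, and SAP 11.2 says that tables will be adapted to the type of event. A copying error is the likelier explanation.
- A reader might see a serious gap in the lack of a rule for missing relatedness. No such rule is stated, but nothing shows that any event lacks an assessment, and the protocol requires queries to be resolved before database lock.

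**Conclusion.** The point holds in a limited form. As listed, the SAP yields no pooled patient-level incidence of adverse events during the study. The patient count can only be bounded from the split tables, and the width depends on overlap: 8 to 14 of 20 in the assumed case of 6 and 8, and narrower when one group is small. This rests on reading the protocol sentence as pooled, on assumed counts, and on a Safety Set of 20. The actual Safety Set may differ, since 20 is stated as the number completing without major deviation.

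Two parts need no such assumption. The SAP's worst-intensity rule is displayed in none of the six tables, and all three unrelated-event shells contradict their titles. No trial conclusion is at risk. This is a reporting improvement together with a label correction, worth making because tolerance is a secondary objective.

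**What to change.** - Add one table on the Safety Set giving the number and percentage of subjects with any treatment-emergent adverse event, incident or expected side effect, by SOC and PT, with worst intensity under the existing 11.2 rule. Keep the split tables beside it.
- Add an all-causality column to the brief summary.
- Correct the headings of 14.3.2.2, 14.3.2.4 and 14.3.2.6 so that they say not related, and replace *Incident* in the rows of 14.3.2.2 with adverse event.
- Align 11.2 with 13.2. Either list the CRS-related and swab-related tables or remove them from the text, and name the unrelated-event SOC/PT table in 11.2.

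The cost is SAP wording, one extra table and one extra column, all from data already collected. No visit, assessment or sample size changes.

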10.1 CRF entry

All the data provided in the protocol and collected by the investigator are to be reported in the case report forms (CRF).

The case report forms will consist of triplicate self-copying sheets (Carbonless copy paper):

- The white sheet (original) is intended for the data entry,
- The blue sheet (median copy) is a working document for reference purpose,
- The yellow sheet (bottom copy) is retained by the investigator.

The CRFs will be completed and signed by the investigator. Each correction will also be initialled and dated by the investigator or his designee.

10.2 Source documents

The investigator is asked to report in the patient's medical record:

- Mention of the subject's participation in the study
- Demographic data (date of birth, sex, name)
- Past medical and surgical history
- Recent past treatments
- Concomitant treatments
- Clinical assessment
- Date of each study visit
- Change in any of the concomitant treatment
- Any adverse event/incident

and all relevant data according to the investigator's opinion.

In case of computerized medical file, a printout will be edited, dated and signed by the investigator.

Source data are documented on the "source data agreement form".

11. Data management

11.1 Methods for data entry and collection

Clinical data related to the study will be collected and saved into a computerized database by the Data Management Department of AXIODIS using the EXAGIS e-CRF software. In order to ensure maximum data quality, the paper CRF will be transcribed into the electronic database using double data entry.

11.2 Data review

After double data entry, a computerized data review will be performed by AXIODIS according to the Data Validation Plan.

Results of this data review will be sent to the Study CRA and/or Study Manager. Whenever required, queries issued from this review will be submitted to the investigator for resolution and signature and then tracked until corrections are entered and validated.

11.3 Data coding

Adverse events, concomitant diseases, medical/surgical histories will be coded by AXIODIS using the MedDRA dictionary (last version in use).

Concomitant medication will be coded using the WHO-DD dictionary (last version in use).

The study manager and/or other relevant sponsor representative will validate the coding.

11.4 Procedures for verification, validation and securing of electronic clinical data system

The EXAGIS software is installed on a Linux server (secure Data Center) hosted at the OVH company that guarantees the security, maintenance, as well as regular antivirus and firewall updates of this dedicated server. Any modification to the data is tracked, i.e. creation and changes are timestamped and authors are recorded. Software access is restricted to authorized users using individual encrypted passwords. Data processing via SAS software (SAS Institute, Cary, NC, USA) is carried out on a Windows 2012 R2 production server at OVH, using direct access by SAS or MySQL Workbench.

11.5 Procedures to maintain and protect subject privacy

Data privacy is ensured through restricted access to the anonymized data located in a dedicated separate database.

11.6 Methods for database locking at the start of analysis and storage upon completion of the clinical investigation

The validated database will be locked upon request of the Data Manager following the completion of all steps required, i.e. resolution of all queries, validation of the coding, data review meeting.

The review process prepared by the clinical research assistant, data manager, study monitor, medical manager and statistician will be concluded during a meeting (Validation Committee) to be attended by at least the following:

- Coordinating investigator,
- Study monitor,
- Sponsor Vigilance representative,
- Study Coordinator,
- Data manager,
- Statistician.

The review is also required for defining the analysis populations and validating the statistical analysis plan.

The meeting will be documented by written and signed minutes that will act as the basis for data processing by the Biometrics Department.

All decisions on the evaluability of the data from each individual subject for the statistical analysis must be made and documented before locking the database.

